5.3.9 Adverse event collection and reporting

AE Collection

The following must be collected and documented on the appropriate / eCRF by the Investigator:

- From signing the informed consent onwards until the end of the REP all AEs (non-serious and serious), and AESIs.
- After the end of the REP until trial completion, all related SAEs and related AESIs.
- If in an individual patient only vital status information is collected from a certain time point on, no further AEs or AESIs will be reported for this patient.

The REP is defined as 42 days (6 weeks) after the last trial medication application. All AEs which occurred through the treatment phase and throughout the REP will be considered as on treatment please see [section 7.3.4](#). Events which occurred after the REP will be considered as post treatment events.

After the last per protocol contact the Investigator does not need to actively monitor patients for AEs. However, if the Investigator becomes aware of SAEs or AESIs that occurred after the last per protocol contact, the SAEs and AESIs should be reported by the Investigator to the Sponsor if considered relevant by the Investigator.

AE reporting to sponsor and timelines

The Investigator must report SAEs, AESIs, and non-serious AEs which are relevant for the reported SAE or AESI, on the BI SAE form via fax immediately (within 24 hours) to the Sponsor's unique entry point (country specific contact details will be provided in the ISF). In specific occasions the Investigator could inform the Sponsor upfront via telephone. This does not replace the requirement to complete and fax the BI SAE form.

With receipt of any further information to these events, a follow-up SAE form has to be provided. For follow-up information the same rules and timeline apply as for initial information.

Information required

For each AE, the Investigator should provide the information requested on the appropriate (e)CRF pages and the BI SAE form, e.g. onset, end date, intensity, treatment required, outcome, seriousness, and action taken with the investigational drug(s). The Investigator should determine the causal relationship to the trial medication.

The following should also be recorded as an (S)AE in the (e)CRF and SAE form (if applicable):

- Worsening of the underlying disease (if not recorded as study endpoint, see exemption below) or of other pre-existing conditions

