6.2.3.2 Residual effect period (REP)

The REP is defined in [Section 5.3.9](#) (6 weeks). The End of REP (EoR) visit should not be performed earlier than 42 days after permanent discontinuation of the trial medication. The information collected at this visit should include all new AEs that occurred after EOT and a follow-up of adverse events ongoing at EOT. Any subsequent anti-cancer therapy administered between EoT and EoR should be reported

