7.3.4 Safety analyses

All patients of the treated set will be included in the safety analyses. Two analyses will be performed. The first analysis of safety will be performed for the first part of the trial

(determination of the MTD, first cycle only, treatment regimen = initial dose at the start of the treatment, treated set). This descriptive analysis will evaluate the MTD for the monotherapy of BI 836880. The second analysis will be performed with respect to all cycles and will act as a support for the determination of the MTD (treated set).

Events that started between the first administration of the treatment until 6 weeks (42 days) after the last administration of treatment will be considered as having occurred on treatment. In general, later events will be attributed to the post-study period and will be presented separately. However, post-study events will be examined to determine whether they need to be combined with on-treatment events in an additional table.

Adverse events will be graded according to CTCAE Version 4.03 ([R12-2532](#)) and reported according to BI standards. *Frequency, severity, and causal relationship of adverse events will be tabulated by system organ class and preferred term after coding according to the current version of the Medical Dictionary for Drug Regulatory Activities (MedDRA).*

Serious adverse events will be tabulated. In addition, events leading to dose reduction or treatment discontinuation will be examined, but may not be reported as individual tables, depending upon the extent of overlap. Descriptive statistics will be used to describe changes in laboratory tests over time. In addition, all abnormalities of potential clinical significance will be reported. In general, potential clinical significance is defined as at least CTCAE Grade 2 and an increase in CTCAE classification from baseline. The incidence and intensity of the more important adverse events (as determined from the analyses above) will be correlated descriptively with pharmacokinetic data, if possible.

Adverse events will be coded using the Medical Dictionary for Regulatory Activities (MedDRA) coding dictionary. Standard BI summary tables and listings will be produced. All adverse events with an onset between start of treatment and end of the residual effect period (REP), a period of 42 days after the last dose of trial medication, will be assigned to the treatment period for evaluation.

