6. GENERAL ANALYSIS DEFINITIONS

6.1 TREATMENT(S)

The starting dose of the study is BI 836880 40mg every three weeks, and dose escalation decision will be made by Data Safety Board (DSB).

The following treatment period will be defined:

- Screening: from the date of informed consent to the date of first study medication intake -1 day.
- On-treatment: from the date of first infusion of study drug to the date of last study drug administration + 42 days, i.e., actual on-treatment period + residual effect period (REP).
- Post-study: from the last day of on-treatment period + 1 day onwards

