7.8.1 Adverse events

The analyses of adverse events (AE) will be descriptive in nature. All analyses of AEs will be based on the number of patients with AEs and not on the number of AEs. Two analyses will be performed. The first analysis of safety will be performed for the first part of the trial (determination of the MTD, first cycle only, dose level = initial dose at the start of the treatment, treated set). This descriptive analysis will evaluate the MTD for the monotherapy

of BI 836880. The second analysis will be performed with respect to all cycles and will act as a support for the determination of the MTD (treated set).

For analysis of duration, severity etc. of multiple AE occurrences, data on the case report form (CRF) will be collapsed into AE episodes provided that all of the following applies:

- The same MedDRA lowest level term was reported for the occurrences.
- The occurrences were time-overlapping or time-adjacent (time-adjacency of two occurrences is given if the second occurrence started on the same day or on the day after the end of the first occurrence).
- Treatment did not change between the onset of the occurrences or treatment changed between the onsets of the occurrences, but no deterioration was observed for the later occurrence.

For further details on summarization of AE data, please refer to the guideline 'Handling and summarization of adverse event data for clinical trial reports and integrated summaries' ([5](#)).

For patients treated with the test drug, that means that all adverse events occurring between first drug infusion and 42 days after last drug infusion or death, whichever occurs first, will be assigned to the on-treatment period. All adverse events occurring before any study drug infusion will be assigned to 'screening' and all adverse events occurring after last study drug infusion + 42 days will be assigned to 'post-study' (for listings only). For details on the treatment definition, see [section 6.1](#).

An overall summary of adverse events will be presented. This summary will exclude the rows 'Severe AEs', 'Significant AEs' and 'Other significant AEs' but will include additional rows for 'AEs leading to dose reduction', 'AEs leading to death' and 'AEs by highest Common Terminology Criteria (CTC) grade'.

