7.8.2 Laboratory data

The analyses of laboratory data will be descriptive in nature and will be based on BI standards “Display and Analysis of Laboratory Data” ([7](#)). CTC grade for applicable lab parameters will be calculated according to CTCAE v4.0 ([6](#)).

Descriptive statistics of all converted laboratory values by visit will be provided including changes from baseline. Frequency tables of transitions relative to the reference range and of possible clinically significant abnormalities will be produced. For those parameters that have CTC grading possible clinically significant abnormalities are defined as those laboratory values with a CTC grade ≥ 2 that have had an increase of ≥ 1 grade from baseline. For those parameters for which no CTC grade has been defined standard BI project definitions will be used to decide on clinical significance. Further frequency table will show the transition of CTC grade from baseline to worst value and last value on treatment.

Summaries will be produced of laboratory data recorded prior to treatment, on-treatment and post-treatment. For details on the treatment definition, see [section 6.1](#).

The focus of the laboratory data analysis will be on the following laboratory parameters:

[figure not shown]
- Low values: Activated Partial Thromboplastin Time (aPTT), Prothrombin Time (PT), International Normalised Ratio (INR), White Blood Cell Count (WBC) with differential, Platelets (PLT)
- High values: Aspartate Aminotransferase (AST), Alanine Aminotransferase (ALT), bilirubin, Alkaline Phosphatase (AP), Activated Partial Thromboplastin Time (aPTT), Prothrombin Time (PT), International Normalised Ratio (INR), Protein levels in urine

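### The 42-day on-treatment period is not split when another anticancer therapy starts, so the all-cycles, all-cause safety tables can contain another regimen's toxicity

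*Protocol*

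**What the plan says.** **The period.** Protocol 5.3.9 fixes the residual effect period: "The REP is defined as 42 days (6 weeks) after the last trial medication application". It adds that "All AEs which occurred through the treatment phase and throughout the REP will be considered as on treatment". Protocol 7.3.4 treats as on treatment "Events that started between the first administration of the treatment until 6 weeks (42 days) after the last administration of treatment". SAP 6.1 gives the period as "from the date of first infusion of study drug to the date of last study drug administration + 42 days", and SAP 7.8.1 assigns to it "all adverse events occurring between first drug infusion and 42 days after last drug infusion or death, whichever occurs first". SAP 7.8.2 refers back to 6.1 for the laboratory periods and plans this display: "Further frequency table will show the transition of CTC grade from baseline to worst value and last value on treatment".

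**Other anticancer therapy.** Under protocol 3.3.4.1, trial drug stops at progression (unless the dose is escalated within the patient) or when a new anticancer therapy starts. Under 6.2.3.3.1, a new therapy also ends follow-up for progression. Protocol 6.2.3.2 says of the weeks before the EoR visit: "Any subsequent anti-cancer therapy administered between EoT and EoR should be reported". None of these sections links the new therapy to the safety period.

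**Use of the tables.** SAP 7.8.1 plans a first-cycle analysis and an all-cycles analysis, and the latter is meant to support the MTD determination. Its tables include all AEs, serious AEs and AEs leading to death by highest CTC grade, irrespective of cause, alongside separate drug-related versions. Protocol 3.1 bases confirmation of the RP2D on safety data from all cycles and all dose levels.

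**The concern.** The plan foresees that a patient may be on another anticancer regimen inside the 42 days and asks for it to be reported, but no visible analysis rule uses that information. An event caused by the next regimen, starting for example on day 35 after the last infusion, is counted as on treatment with BI 836880. In the all-cause tables it looks the same as an event that arose under BI 836880 alone. Laboratory shift tables have no causality filter at all.

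At stake is how the all-cycles tables are read, as tolerability beyond cycle 1 and as support for the dose. Protocol 3.1 allows dose cohorts of 2 patients, so one such event can dominate a row. The handling is also one-sided. Protocol 7.3.4 provides for looking at whether post-study events should be combined with on-treatment ones, but not for separating events that follow a new drug.

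**Working it through.** **Inputs from the documents**
- REP: 42 days (protocol 5.3.9 and 7.3.4; SAP 6.1 and 7.8.1).
- Cycle length: 21 days (protocol 6.2.2).
- Imaging: day 18, plus or minus 3 days, of courses 2, 4 and 6 (flow chart).
- Patients at the MTD: at least 12 (synopsis). Minimum dose cohort: 2 (protocol 3.1).

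**1. The plan's own figure.** 6 weeks x 7 = 42 days. The four sections agree.

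**2. What ends the period early.** Protocol 5.3.9 and 7.3.4 and SAP 6.1 name nothing. SAP 7.8.1 names death. New anticancer therapy is named in none of them.

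**3. Room for overlap after progression.** Day 18 of a course is 18 - 1 = 17 days after that course's infusion (14 to 20 with the visit window). This leaves 42 - 17 = 25 days (22 to 28) of on-treatment period after the scan. For course 2, the scan is on trial day 21 + 18 = 39, the last infusion was on day 22, and the period ends on day 22 + 42 = 64. A switch in that time is plausible. Exclusion criterion 2 of this trial itself accepts patients 28 days after their previous systemic therapy, or after 5 half-lives if that is shorter.

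**4. Share of the period under the next regimen.** With k infusions the period lasts D = 21 x (k - 1) + 42 days. If the next therapy starts s days after the last infusion, the overlap is 42 - s days. The values of s are assumed.

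| Infusions k | D (days) | s = 21 | s = 28 | s = 35 |
|---|---|---|---|---|
| 2 | 63 | 21/63 = 33% | 14/63 = 22% | 7/63 = 11% |
| 4 | 105 | 21/105 = 20% | 14/105 = 13% | 7/105 = 7% |
| 6 | 147 | 21/147 = 14% | 14/147 = 10% | 7/147 = 5% |

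These are shares of one switching patient's time, not event rates.

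**5. Patients affected (illustration only).** Let p be the proportion starting a new therapy inside the REP. Let q be the chance that this therapy causes a tabulated AE before day 42. The documents give neither, so p = 10% to 50% and q = 10% to 40% are assumptions.
- Affected share p x q: 0.10 x 0.10 = 1% up to 0.50 x 0.40 = 20%.
- Expected number of 12 at the MTD: 12 x 0.01 = 0.12 up to 12 x 0.20 = 2.4.
- Chance of at least one of 12, 1 - (1 - pq)^12: 1 - 0.99^12 = 11% up to 1 - 0.80^12 = 93%.
- With p = 30% and q = 20%: 12 x 0.06 = 0.72 patients, and 1 - 0.94^12 = 52%.

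One affected patient is 1/12 = 8 percentage points at the MTD and 1/2 = 50 points in a cohort of 2. These are upper limits for an overall row by highest grade, because a patient with an earlier event of equal or worse grade adds nothing there.

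**6. Laboratory values.** As far as the flow chart can be read, the safety laboratory row ends at EoT, and protocol 6.2.3.2 lists only AEs and new therapy for the EoR visit. EoT may fall up to 3 weeks after discontinuation (6.2.3.1). The follow-up visits for which 3.3.4.1 makes safety laboratory tests mandatory come after EoR (6.2.3.3.1), outside the 42 days. Exposed values therefore come mainly from a late EoT or from unscheduled tests.

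**The case against.** The strongest reply is that attribution is already handled. Under protocol 5.3.8.1 every AE receives a causality assessment that must weigh confounders such as concomitant medication, with the reason recorded. SAP 7.8.1 tabulates drug-related AEs and drug-related serious AEs separately, and the only safety secondary endpoint is confined to drug-related events. All-cause tables include unrelated events by design. This stands for the drug-related tables. It does not show a reader how much of an all-cause row arose after a switch, and it covers laboratory tables only where a change was also recorded as an AE.

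A second reply is that removing post-switch events assessed as unrelated from the main tables would weaken them as a causality-free check. This is a first-in-human trial of a molecule built for a longer half-life, and late toxicity wrongly ascribed to the next drug would drop out. This stands, and it is why the change should be supplementary.

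Third, parts of the planning are not visible: SAP 5.4, the technical TSAP and the sponsor guideline on AE summaries. They might hold a flag or listing. The definitions printed in SAP 6.1 and 7.8.1 nevertheless contain no such split.

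A reader might also infer that the MTD itself is contaminated. The documents do not support that. Protocol 5.1.1 and SAP 7.4 base it on DLTs in the evaluation period after the first dose, and 5.1.1 requires them to be drug-related.

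**Conclusion.** The gap is real but limited. The all-cycles, all-cause AE tables can contain another regimen's toxicity. Laboratory worst and last values can as well, to a lesser extent. The primary MTD analysis is not affected, and the drug-related tables are largely protected by the causality assessment.

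The size is unknown because the documents give no switching rate. The 0.12 to 2.4 of 12 patients, and the 11% to 93% chance of at least one, depend wholly on the assumed p and q.

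A reader might go further and infer that patients at low doses switch sooner, so that the contamination raises low-dose rates most and flattens the dose-toxicity gradient. Protocol 4.1.3 does call doses below the target concentration non-therapeutic, but no section says when patients at any dose switch. Intra-patient escalation is allowed, and early stopping for toxicity at high doses could push the difference the other way. Its direction is therefore as unknown as its size.

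The change is worth making because the all-cycles analysis is stated to support the MTD and the remedy is cheap.

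**What to change.** Leave AE collection and the main 42-day tables unchanged. In SAP 7.8.1 and 7.8.2:
- Derive a flag from the start date of the next anticancer therapy. Protocol 6.2.3.2 requires the therapy to be reported but does not mention a date, so confirm that the eCRF captures one, and state how partial dates are handled.
- Show the all-AE, serious-AE, fatal-AE and CTC-grade tables, and the laboratory worst and last on-treatment values, a second time with the period ending at the earlier of day 42 and that start date.
- Show events starting after that date, up to day 42, in a separate column or listing with their causality.

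If the date is in the database, no new data are needed and no event is lost. The cost is SAP wording, one derived variable and one extra column or supplementary table set. If the database is already locked, the same displays can be added as supplementary output.

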2.3 BENEFIT - RISK ASSESSMENT

BI 836880 has not been tested in human so far. In the 13 weeks toxicology study in cynomolgus monkeys BI 836880 was well tolerated up to the highest tested dose of 60 mg/kg.

Anti-VEGF or anti-VEGF-R antibodies have been largely tested in clinic with a well-defined safety profile. Most commonly reported adverse events with such compounds are fatigue, hypertension, proteinuria, diarrhea and bleeding (epistaxis). Severe adverse events include gastrointestinal perforations, tumor haemorrhage and arterial thromboembolism ([R14-3588](#), [R14-3261](#)).

There is less clinical experience with anti-Ang2 compared to VEGF pathway blockade clinical experience. The most advanced anti-angiopoietin compound (Trebaninib) in development is in Phase III in combination with chemotherapy [R14-5440](#). Other anti-Ang2 compounds are currently in early stage of clinical development ([R15-1645](#), [R15-1646](#), [R15-1648](#)). From this clinical experience the most commonly reported side effects are fatigue and gastro-intestinal symptoms (diarrhea, nausea and vomiting). No bleeding or thromboembolic events were reported with this class of compound. Of note, almost all tested anti-Ang2 molecules failed to define a MTD ([R15-1646](#), [R15-1648](#)).

Limited clinical experience of dual blockade is available. Recently, Phase I data of the bispecific human anti-Ang2/anti VEGF-A antibody (RG7221) were reported. MTD was not reached with only one dose limiting toxicity (DLT) reported (fatal pulmonary hemorrhage). Hypertension was the most common observed adverse event ([R15-1644](#)).

Based on this clinical available data it is expected that blockade of both targets will result in similar side effects as anti-VEGF and anti-Ang2 blockade. Based on the phase I trial results of RG7221 no increase in side effect severity is anticipated with BI 836880. It is anticipated that the safety profile of BI 836880 will most likely includes fatigue, hypertension, proteinuria, gastro-intestinal side effects and bleeding.

Previous clinical experience with nanobodies in different disease showed acceptable safety profile with no specific side effect related to this technology ([R13-2303](#)).

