In case of clinical symptoms of hepatic injury (icterus, unexplained encephalopathy, unexplained coagulopathy, right upper quadrant abdominal pain, etc.) without lab results (ALT, AST, total bilirubin) available, the investigator should make sure these parameters are analysed, if necessary in an unscheduled blood test. Should the results meet the criteria of hepatic injury alert, the procedures described in the DILI checklist should be followed.

Dose Limiting Toxicities:

Any medical event fulfilling the criteria of DLT (see [section 5.3.1](#)) should be reported by Investigator as AESI.

Intensity of AEs

The intensity of the AE should be judged based on the following:

The intensity of adverse events should be classified and recorded in the (e)CRF according to the Common Terminology Criteria for Adverse Events (CTCAE) Version 4.0 (v4.03: June 14, 2010) ([R12-2532](#)).

Causal relationship of AEs

Medical judgment should be used to determine the relationship, considering all relevant factors, including pattern of reaction, temporal relationship, de-challenge or re-challenge, confounding factors such as concomitant medication, concomitant diseases and relevant history.

Yes: There is a reasonable causal relationship between the investigational product administered and the AE.

No: There is no reasonable causal relationship between the investigational product administered and the AE.

The causal relationship must be provided by the Investigator for all potential trial drugs, i.e. the BI trial drug and for all other trial drugs (such as any active comparator or placebo).

[figure not shown]
The reason for the decision on causal relationship needs to be provided in the (e)CRF and on the SAE form (if applicable).

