- Changes in vital signs, ECG, physical examination and laboratory test results, if they are judged clinically relevant by the Investigator.

If such abnormalities already pre-exist prior trial inclusion they will be considered as baseline conditions.

All (S)AEs, including those persisting after trial completion must be followed up until they have resolved, have been sufficiently characterized, or no further information can be obtained.

Pregnancy

In the rare case that a female subject participating in this clinical trial becomes pregnant after having taken trial medication, the Investigator must report immediately (within 24 hours) the drug exposure during pregnancy (DEDP) to the Sponsor's unique entry point (country-specific contact details will be provided in the ISF). The Pregnancy Monitoring Form for Clinical Trials (Part A) should be used.

The outcome of the pregnancy associated with the drug exposure during pregnancy must be followed up and reported to the Sponsor's unique entry point on the Pregnancy Monitoring Form for Clinical Trials (Part B).

As pregnancy itself is not to be reported as an AE, in the absence of an accompanying SAE, only the Pregnancy Monitoring Form for Clinical Trials and not the SAE form is to be completed. If there is an SAE associated with the pregnancy then the SAE has to be reported on the SAE form in addition.

The ISF will contain the Pregnancy Monitoring Form for Clinical Trials (Part A and B).

Exemptions to (S)AE Reporting

Disease Progression in oncology trials is a study endpoint for analysis of efficacy and as such is exempted from reporting as an (S)AE. Progression of the subject's underlying malignancy will be recorded on the appropriate pages of the (e)CRF as part of efficacy data collection only and will not be reported on the SAE Form. It will therefore not be entered in the safety database (ARISg) and hence not get expeditiously reported. Death due to disease progression is also to be recorded on the appropriate (e)CRF page and not on the SAE Form.

Examples of exempted events of PD may be:

- Progression of underlying malignancy (Progressive disease [PD]): if PD is clearly consistent with the suspected progression of the underlying malignancy as defined by the respective response criteria.
- Hospitalization/Procedures due solely to the progression of underlying malignancy (PD)

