- Clinical symptoms and/or signs of progression (without confirmation by objective criteria e.g. imaging, clinical measurement): if the symptom can exclusively be determined to be due to the progression of the underlying malignancy and does meet the expected pattern of progression for the disease under study.

However, when there is evidence suggesting a causal relationship between the study drug(s) and the progression of the underlying malignancy, the event must be reported as an (S)AE on the SAE Form and on the (e)CRF.

Exempted events are collected and tracked following a protocol-specified monitoring plan. Exempted events are monitored at appropriate intervals preferably by an independent committee such as a Data Safety Board.

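### Deaths attributed to progression leave the SAE form with no 'solely' test, and the override asks whether the drug caused the progression, not the event, so a fatal tumour-site bleed or perforation may go unrecorded as an AE

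*Protocol*

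**What the plan says.** Protocol 5.3.9, under the exemptions to (S)AE reporting, treats progression as an efficacy endpoint and takes it off the SAE form. Of progression it says: "It will therefore not be entered in the safety database (ARISg) and hence not get expeditiously reported". It then sets different conditions for different events:

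- Death: "Death due to disease progression is also to be recorded on the appropriate (e)CRF page and not on the SAE Form".
- Hospital stay or procedure: "Hospitalization/Procedures due solely to the progression of underlying malignancy (PD").
- Symptom or sign without objective confirmation: exempt "if the symptom can exclusively be determined to be due to the progression of the underlying malignancy", and only if it also fits the expected course of the disease.
- Override: the event goes back on the SAE form "when there is evidence suggesting a causal relationship between the study drug(s) and the progression of the underlying malignancy".

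The same section says that exempted events are gathered and followed under a monitoring plan, and adds: "Exempted events are monitored at appropriate intervals preferably by an independent committee such as a Data Safety Board".

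The general rules also matter. Section 5.3.8.1 defines an AE without regard to cause and makes it serious if it is fatal. It requires a CTCAE grade for each AE and, on causality, says: "The reason for the decision on causal relationship needs to be provided in the (e)CRF". Section 5.3.9 requires all AEs to be collected from consent to the end of the residual effect period, 42 days after the last dose. SAP 7.8.1 tabulates serious AEs and AEs leading to death.

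**The concern.** The drug blocks VEGF-A and Ang2. Protocol 2.3 lists tumour haemorrhage and gastrointestinal perforation among the severe harms of anti-VEGF agents and expects bleeding with BI 836880. Of the other bispecific against the same two targets it reports: "MTD was not reached with only one dose limiting toxicity (DLT) reported (fatal pulmonary hemorrhage").

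Such a drug can make a tumour bleed, or a tumour-bearing organ perforate, without making the cancer grow. The override's question, whether the drug caused the progression, is then answered no even if the drug caused the bleed. For deaths, no other condition stands behind it.

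At stake is whether a first-in-human trial's safety record shows the very kind of event that was the comparator's only DLT. If it is classed as progression, it can be missing from the safety database, from expedited reporting and from the SAP's death and serious-event tables.

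**Working it through.** This is a check of the text. The plan states no figure on this point, so there is none to reproduce.

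**Step 1. The conditions side by side (Protocol 5.3.9).**

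| Event attributed to progression | Condition for exemption | Does suspected drug contribution to the event defeat it? |
|---|---|---|
| Hospitalisation or procedure | due solely to progression | Yes |
| Unconfirmed symptom or sign | due exclusively to progression, and expected pattern | Yes |
| Death | due to progression, no qualifier | Not stated |
| Override for all | drug may have caused the progression | No; it asks about a different causal link |

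**Step 2. Non-fatal tumour-site bleed.** It is an AE under 5.3.8.1 and must be collected under 5.3.9. To be exempt as a sign, it must be exclusively due to progression. An investigator who suspects any drug contribution cannot say that. What is left is misattribution, made without a recorded reason because the duty in 5.3.8.1 attaches to AEs. The gap is small.

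**Step 3. Fatal tumour-site bleed in a patient judged to have died of progression.** The death meets the unqualified sentence and stays off the SAE form. The override does not bring it back unless the drug is thought to have caused the progression. The bleed, taken as a sign, should still face the exclusivity condition, but 5.3.9 does not say that the event leading to an exempted death is recorded separately. A site could reasonably complete the death page alone.

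**Step 4. What the record then holds.** The death is on an eCRF page. The text requires no CTCAE grade and no causality reason for an exempted event. The SAP 7.8.1 tables count patients with AEs, so with no AE record there is no entry in them.

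**Step 5. Illustration of one lost record.** Exact (Clopper–Pearson) two-sided 95% limits:

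- 0 of n, upper limit: 1 − 0.025^(1/n).
- 1 of n, lower limit: 1 − 0.975^(1/n).
- 1 of n, upper limit: the p that solves (1−p)^n + n·p·(1−p)^(n−1) = 0.025.

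| Group (source) | n | One event recorded | None recorded | Fall in upper limit |
|---|---|---|---|---|
| Proposed RP2D, up to 12 (Protocol 3.1, 5.3.2) | 12 | 8.3% (0.2–38.5%) | 0% (0–26.5%) | 38.48 − 26.46 = 12.0 points |
| Tumour-type cohort, up to 20 (Protocol 3.1) | 20 | 5.0% (0.1–24.9%) | 0% (0–16.8%) | 24.87 − 16.84 = 8.0 points |
| Whole trial, about 80 (synopsis, 3.3) | 80 | 1.3% (0.03–6.8%) | 0% (0–4.5%) | 6.77 − 4.51 = 2.3 points |

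These figures only restate the loss of one hypothetical event; they are no evidence that it occurs. The denominators are planned numbers, and Protocol 3.1 makes the tumour-type cohorts depend on a further amendment.

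**The case against.** The strongest reply is that 5.3.9 exempts progression and death from progression, not bleeding. A haemorrhage is an untoward event, must be collected up to 42 days after the last dose, and is serious if fatal. An investigator who has read section 2.3 could hardly call it exclusively due to progression. This stands for non-fatal events. For fatal ones it shows that the better reading is to record the bleed, but the section does not say so.

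A second reply is that nothing vanishes. Exempted events are tracked, the reason for death is among the follow-up data (6.2.3.3.1), and the DSB reviews overall safety. That also stands, with two limits. The supplied text does not set out the monitoring plan. Committee review is only preferably independent, and this trial's DSB consists of investigators and sponsor representatives (Protocol 3.1.1, 7.4).

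A third reply is that unseen sources may close the gap. The list of always-serious events (5.3.8.1) was not supplied and might name these events, although 5.3.9 does not say which rule prevails. The content of the death page is unknown too, so one can say only that a grade and a causality reason are not required there, not that they are absent.

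A reader might go further and infer that lost events would distort dose escalation. The documents do not support that. Whether an event is a DLT turns on the drug-relatedness judgement in 5.3.1, which the exemption does not alter. The first scheduled on-treatment imaging in the flow chart is in course 2, so a cycle 1 event called progression would normally face the strict symptom condition.

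**Conclusion.** The point holds in a narrow form and at low severity. The death exemption lacks the qualifier given to its neighbours, and the override asks the wrong causal question for a harm that the protocol itself expects. The remaining exposure is mainly a fatal tumour-site haemorrhage or perforation in a patient whose death is attributed to progression. Its size is one missing SAE record and one missing entry in the death table per such event. No rate can be derived from the documents, and no effect on the MTD model is shown.

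It would be too strong to read 5.3.9 as exempting haemorrhages and perforations in general; the solely and exclusively conditions and the AE collection rule prevent that.

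The conclusion assumes that neither the always-serious list nor the monitoring plan already requires these events to be reported as SAEs. If either does, what remains is a matter of clarifying precedence.

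**What to change.** 1. Protocol 5.3.9, override: change the causal link to 'between the study drug(s) and the event or the progression'.
2. Protocol 5.3.9, death sentence: restrict it to 'death due solely to disease progression, with no suspected contribution of BI 836880'.
3. Protocol 5.3.9: state that haemorrhage and organ perforation are always recorded as AE/SAE with CTCAE grade and causality, whether or not progression is present. Edits 1 and 2 still rely on the investigator suspecting the drug; this one does not.
4. SAP 7.8.1: add a by-dose listing of deaths attributed to progression within 42 days of the last dose.

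**Cost.** No new visits. The wording edits need an amendment with ethics and authority approval (Protocol 8.1), and a few disease-related bleeds will be reported as SAEs. Version 6.0 refers to two ongoing patients, so the edits act mainly on them and on any later enrolment. The listing may therefore be worth the most: it can be built from death and dosing data already collected and covers patients already treated, although it cannot supply a grade or causality reason that was never recorded.
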